5.2.2.2 Vital Signs

Vital signs have been recorded at Visit 1, Visit 2, Visit 3, Visit 4, Visit 5.

Collected Variables:

- Systolic blood pressure (mmHg) [CRF – Visit 1, 2, 3, 4, 5]
- Diastolic blood pressure (mmHg) [CRF – Visit 1, 2, 3, 4, 5]
- Heart rate (beats/min) [CRF – Visit 1, 2, 3, 4, 5]
- Respiratory rate (acts/min) [CRF – Visit 1, 2, 3, 4, 5]
- Temperature (°C) [CRF – Visit 1, 2, 3, 4, 5]

Derived Variables:

- Change from Baseline will be derived as follows:

Absolute change (unit) = Value at Visit X – Baseline Value

	Form	Form No.	1M-DMST-011-01-A1
	Statistical Analysis Plan	Page	Page 27 of 69
		Effective Date	07/05/2018

$$\text{Relative change (\%)} = \frac{\text{Value at Visit X} - \text{Baseline Value}}{\text{Baseline Value}} \times 100$$

Analysis Sets to be used for:	Tables	Safety analysis set
	Listings	Safety analysis set
	Figures	Not applicable

Vitals signs will be summarized as follows:

Table 24. Summary of Vital Signs (Safety set)

Summary of quantitative vital signs assessments will be presented by treatment group using default summary statistics. At each assessed visit, summary statistics will be presented also for the change from baseline at each post-baseline visit.

In addition to the tables the vital signs will be presented in subject data listings as follows:

Listing 22. Vital Signs in the Multidose Phase Vital signs data will be presented by-subject and within-subject by visit.

Listing 23. Vital Signs in the single dose phase Vital signs data in the single dose phase will be presented by subject.

Graphical representation of the trend over the whole study of each vital sign will be provided by means of line graphs.

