3.2 Flow Chart

	V1 Screening & treatment start					V2	V3	V4	V5 (EOS)	
	Day -7					Day 0	Day 7	Day 14	Day 28	
	moment 0	h 1	h 2	h 4	h 8	h 12				
ICF	x									
Incusion/Exclusion criteria check	x									
Vital signs	x	x	x	x	x	x	x	x	x	x
Physical examination	x						x	x	x	x
Medical history	x									
Concomitant medication	x						x	x	x	x
Blood sampling	x	x	x	x	x	x	x	x	x	x
CoQ10 intake	x						AB	AB	AB	AB
Pharmacokinetics		x	x	x	x	x	x	x	x	x
Adverse events		x	x	x	x	x	x	x	x	x

	Study Title	Bioavailability Study of COQUN ORAL FORMULATION (CoQ10) administered in Healthy Adults (CoQ10-01)		
	Study ID	VF-BAQ10/2018	Sponsor:	VISUFARMA SpA
	Date	March 03, 2018	Vers.	Final

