12.8 Analysis of Secondary Variables

The secondary variables are the ones regarding safety which will be monitored through vital signs, physical exams, ECGs, clinical laboratory tests and adverse events, as follows:

- Following a single oral dose of 100mg COQUN ORAL FORMULATION
- in 1 month period of daily oral intake of 100mg OD or BID COQUN ORAL FORMULATION

Symptoms and signs like mild insomnia, elevated levels of liver enzymes, rash, nausea, upper abdominal pain, dizziness, sensitivity to light, irritability, headache, heartburn, and fatigue will be closely monitored.

At each time point and for each group, descriptive statistics will be provided. See section **12.9** for details.

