4.3 Visit Names and Labels

The names to be used in the analysis datasets and the labels to be used in the tables, listings and figures for the different study visits are defined below.

Visit number	Visit name	Visit label, which appear in TLFs
V1-H0	Visit 1: assessment moment 0 (before COQUN intake)	Visit 1 – Hour 0
V1-H1	Visit 1: assessment hour 1	Visit 1 – Hour 1
V1-H2	Visit 1: assessment hour 2	Visit 1 – Hour 2
V1-H4	Visit 1: assessment hour 4	Visit 1 – Hour 4
V1-H8	Visit 1: assessment hour 8	Visit 1 – Hour 8
V1-H12	Visit 1: assessment hour 12	Visit 1 – Hour 12
V2	Visit 2 - Day 0	Visit 2
V3	Visit 3 - Day 7	Visit 3
V4	Visit 4 - Day 14	Visit 4
V5	Visit 5 - Day 28 (EOS)	Visit 5

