4.4 Study periods, Baseline and Endpoint Values

- First date of medication administration

Day 1 date (collected in patients' V2-V5 diary) will be treated as first intake of study medication.

- Last date of medication administration

Day 28 date (collected in patients' V2-V5 diary) will be treated as last intake of study medication (if the subject completes the study this date should coincide with the date of last investigational product intake).

If the date of last intake of study medication is not available, due to premature termination or other reasons, date of last investigational product intake (collected in the end of study form of the CRF) will be imputed.

- Duration of study medication treatment

Duration (days) = Date of last medication administration - Date of first medication administration + 1

- Baseline value

The baseline value for a variable is defined as the last non-missing value collected before first study medication administration. In the single dose phase, the moment 0 (visit 1- hour 0) will be considered as baseline value while in the multidose phase, baseline will be visit 2 (day 0) if not specified otherwise.

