5.2.2 Analysis of Secondary Variables

	Form	Form No.	1M-DMST-011-01-A1
	Statistical Analysis Plan	Page	Page 24 of 69
		Effective Date	07/05/2018

Secondary objectives of this study are:

- To evaluate the safety and tolerability COQUN ORAL FORMULATION following single dose of 100mg
- To evaluate the safety and tolerability of COQUN ORAL FORMULATION during the 1 month daily dose

The secondary variables are the ones regarding safety which will be monitored through:

- Vital signs
- Adverse events

Special interest will be paid on symptoms and signs like mild insomnia, elevated levels of liver enzymes, rash, nausea, upper abdominal pain, dizziness, sensitivity to light, irritability, headache, heartburn, and fatigue.

Analysis of safety will be performed on the safety analysis set.

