Visit 1	n	XX	XX	XX
	Mean (SD)	X.X (X.XX)	X.X (X.XX)	X.X (X.XX)
	Median	X.X	X.X	X.X
	Min/Max	X.X/X.X	X.X/X.X	X.X/X.X
Visit 2 (Baseline)	n	XX	XX	XX
	Mean (SD)	X.X (X.XX)	X.X (X.XX)	X.X (X.XX)
	Median	X.X	X.X	X.X
	Min/Max	X.X/X.X	X.X/X.X	X.X/X.X
Visit 3	n	XX	XX	XX
	Mean (SD)	X.X (X.XX)	X.X (X.XX)	X.X (X.XX)
	Median	X.X	X.X	X.X
	Min/Max	X.X/X.X	X.X/X.X	X.X/X.X
Absolute Change from baseline at Visit 3	n	XX	XX	XX
	Mean (SD)	X.X (X.XX)	X.X (X.XX)	X.X (X.XX)
	Median	X.X	X.X	X.X
	Min/Max	X.X/X.X	X.X/X.X	X.X/X.X
Relative Change from baseline at Visit 3	n	XX	XX	XX
	Mean (SD)	X.X (X.XX)	X.X (X.XX)	X.X (X.XX)
	Median	X.X	X.X	X.X
	Min/Max	X.X/X.X	X.X/X.X	X.X/X.X
Visit 4	n	XX	XX	XX
	Mean (SD)	X.X (X.XX)	X.X (X.XX)	X.X (X.XX)
	Median	X.X	X.X	X.X
	Min/Max	X.X/X.X	X.X/X.X	X.X/X.X
Absolute Change from baseline at Visit 4	n	XX	XX	XX
	Mean (SD)	X.X (X.XX)	X.X (X.XX)	X.X (X.XX)
	Median	X.X	X.X	X.X
	Min/Max	X.X/X.X	X.X/X.X	X.X/X.X
Relative Change from baseline at Visit 4	n	XX	XX	XX
	Mean (SD)	X.X (X.XX)	X.X (X.XX)	X.X (X.XX)
	Median	X.X	X.X	X.X
	Min/Max	X.X/X.X	X.X/X.X	X.X/X.X
Visit 5	n	XX	XX	XX
	Mean (SD)	X.X (X.XX)	X.X (X.XX)	X.X (X.XX)
	Median	X.X	X.X	X.X
	Min/Max	X.X/X.X	X.X/X.X	X.X/X.X
Absolute Change from baseline at Visit 5	n	XX	XX	XX
	Mean (SD)	X.X (X.XX)	X.X (X.XX)	X.X (X.XX)
	Median	X.X	X.X	X.X
	Min/Max	X.X/X.X	X.X/X.X	X.X/X.X
Relative Change from baseline at Visit 5	n	XX	XX	XX
	Mean (SD)	X.X (X.XX)	X.X (X.XX)	X.X (X.XX)
	Median	X.X	X.X	X.X
	Min/Max	X.X/X.X	X.X/X.X	X.X/X.X

N: Number of subjects in specified treatment group

n: Number of subjects with data available

SD = Standard deviation

Note: a) Baseline is defined as value observed at Visit 2.

 Regulatory & Clinical Development	Form	Form No.	1M-DMST-011-01-A1
	Statistical Analysis Plan	Page	Page 52 of 69
		Effective Date	07/05/2018

Table 25. Plasma Concentration of Q10 in the Single Dose Phase (ITT Analysis Set)

Plasma Concentration of Coenzyme Q10

Visit 1	Statistic	Total (N=XXX)
Visit 1 - H0	n	XX
	Mean (SD)	X.XXX (XX.XX)
	95% CI	XX.X/XX.X
	CV (%)	XX.XX
	Median	X.XXX
	Interquartile	
	Range	XX.X
	Min/Max	XX.XX/XX.XX
Visit 1 - H1	n	XX
	Mean (SD)	X.XXX (XX.XX)
	95% CI	XX.X/XX.X
	CV (%)	XX.XX
	Median	X.XXX
	Interquartile	
	Range	XX.X
	Min/Max	XX.XX/XX.XX
Visit 1 - H2	n	XX
	Mean (SD)	X.XXX (XX.XX)
	95% CI	XX.X/XX.X
	CV (%)	XX.XX
	Median	X.XXX
	Interquartile	
	Range	XX.X
	Min/Max	XX.XX/XX.XX
Visit 1 - H4	n	XX
	Mean (SD)	X.XXX (XX.XX)
	95% CI	XX.X/XX.X
	CV (%)	XX.XX
	Median	X.XXX
	Interquartile	
	Range	XX.X

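### Vital signs are scheduled before and five times after the single dose, but the SAP's only vital-signs table summarises neither the hourly values nor the change from pre-dose

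*SAP*

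**What the plan says.** The protocol's flow chart (3.2) has ten columns: moment 0 and hours 1, 2, 4, 8 and 12 of Day -7, then V2 to V5. The vital-signs line is marked in all ten: "Vital signs x x x x x x x x x x".

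Safety after the single dose is a secondary objective, repeated in SAP 5.2.2: "To evaluate the safety and tolerability COQUN ORAL FORMULATION following single dose of 100mg". Protocol 12.8 names vital signs among the variables for that objective and sets the rule: "At each time point and for each group, descriptive statistics will be provided".

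SAP 4.3 gives each of the six Visit 1 times its own label (V1-H0 to V1-H12) and identifies V1-H0 as taken before intake. SAP 4.4 sets the baseline: "In the single dose phase, the moment 0 (visit 1- hour 0) will be considered as baseline value". For the multidose phase, baseline is Visit 2 unless specified otherwise.

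SAP 5.2.2.2 then works by visit only: "Vital signs have been recorded at Visit 1, Visit 2, Visit 3, Visit 4, Visit 5". Its single table is described with "At each assessed visit, summary statistics will be presented also for the change from baseline at each post-baseline visit". The Table 24 template has one Visit 1 row, a Visit 2 row marked as baseline, rows for Visits 3, 4 and 5, and absolute and relative change rows at those last three visits. Its footnote reads "Note: a) Baseline is defined as value observed at Visit 2". SAP 6 declares no change from the protocol's analysis.

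**The concern.** The readings that bear most directly on safety after the single dose are those at hours 1 to 12, compared with hour 0. The plan schedules them, labels the hours and names the right baseline, but no vital-signs table uses any of this. A reader of the study report would see one Visit 1 summary per vital sign, of unstated timing, and then a baseline taken a week after the dose.

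SAP 5.2.2 narrows the secondary variables to vital signs and adverse events. Vital signs are therefore the only measured safety quantity that the SAP analyses for the single-dose phase. A modest average fall or rise in blood pressure or heart rate over the 12 hours, too small in any one subject to be called clinically significant, is what a group summary is meant to show. As planned, it would be in no table.

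**Working it through.** The plan gives no figure of its own on this point, so the check compares what is scheduled with what is tabulated.

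**Inputs.** Time points: protocol 3.2. Subjects: 24 (protocol 12.3). Vital signs: systolic and diastolic pressure, heart rate, respiratory rate and temperature, so 5 (SAP 5.2.2.2). Rows: Table 24 template (SAP 8.2.1.3). Lists of tables and figures: SAP 8.1.1 and 8.1.3.

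**Schedule against Table 24, per vital sign**

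| | Scheduled | In Table 24 |
|---|---|---|
| Single-dose time points (V1) | 6 (1 pre-dose, 5 post-dose) | 1 row, time not stated |
| Multidose visits (V2 to V5) | 4 | 4 rows |
| Total levels | 6 + 4 = 10 | 1 + 4 = 5 |
| Change after the single dose, against V1-H0 | 5 possible | 0 |
| Change in the multidose phase, against V2 | 3 possible (V3, V4, V5) | 3 |

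**Size.** Post-dose values scheduled on Day -7: 24 subjects × 5 hours × 5 vital signs = 600, assuming every subject attends and every reading is taken. Each single hour contributes 24 × 5 = 120. If the Visit 1 row holds the pre-dose reading, none of the 600 enters a table. If it holds one post-dose hour, 120 do and 480 do not. The SAP does not say which applies.

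**Other outputs.**

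1. None of the other 27 tables in SAP 8.1.1 covers vital signs.
2. Listing 23 covers the single-dose phase by subject. Its template rows read Visit 1 with no hour, and a listing gives no descriptive statistics.
3. SAP 5.2.2.2 promises line graphs of each vital sign over the study. The same section marks figures as not applicable, and none of Figures 1 to 7 shows vital signs.

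**Comparison within the SAP.** For CoQ10 concentration, Tables 25 and 26 have a row for each of the six Visit 1 times, and Table 27 gives change from V1-H0 at each post-dose hour. The hourly layout already exists for concentration but was not carried over to vital signs.

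**The case against.** The strongest reply is that a material change would not be lost. Protocol 11.1.1 makes any clinically significant change in vital signs an adverse event and lets the investigator record a trend as one. Single-dose adverse events are counted in Tables 18, 22 and 23 and itemised in Listing 18. This stands. A reader might infer that a post-dose fall in blood pressure would appear in no table, and the documents do not support that. What is missing is the group-level and sub-clinical picture.

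Other parts of the reply also stand:

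- SAP 4.3 provides hour labels for tables, listings and figures, so the Visit column of Listing 23 could carry them. A two-row placeholder does not prove that the listing will lack times.
- Protocol 12.8 asks for descriptive statistics, not change. Missing hourly levels depart from the protocol. Missing hourly change is a mismatch within the SAP, which defines a single-dose baseline that no vital-signs table uses.
- The hourly schedule for vital signs rests on the flow chart. Protocol 10.5.1 lists vital signs once and adds that safety is followed throughout the day; 10.6.5 gives no hours. The case report form is not available, so 600 is a ceiling on values scheduled, not a count of values collected.
- The study is exploratory and tests no pre-specified hypothesis.

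Other stronger readings also fail. A reader might take the Visit 1 row to be an average of all six readings, diluting any effect; no text proposes averaging, and the template defines n as subjects with data. A reader might say that no change on treatment is summarised at all; multidose change at Visits 3 to 5 is. A reader might call vital signs the only objective measure repeated after the dose; protocol 10.6.12 also plans haematology samples on Day -7. Hypotension is an exclusion criterion, but it is not among the listed events of special interest, so the documents do not present it as an expected effect.

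The general baseline rule in SAP 4.4 does not rescue Table 24. The template's footnote fixes Visit 2, and there are no hourly rows to which the rule could apply.

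**Conclusion.** The point holds for the single-dose phase. Followed as written, the SAP produces no hourly summary of vital signs and no change from pre-dose: 0 of 5 post-dose hours, with up to 600 scheduled values affected, assuming full attendance and collection as in the flow chart. It also leaves undefined which of six readings fills the Visit 1 row. The missing hourly levels depart from protocol 12.8 without being declared in SAP 6.

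The consequence is limited. Clinically significant changes can still be counted as adverse events, the data are to be listed, and multidose change is summarised. What is lost is any tabulated view of average or sub-clinical shifts over the 12 hours, for a stated secondary objective. That is worth correcting before the SAP is signed.

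**What to change.** 1. Add a table of vital signs in the single-dose phase, with rows V1-H0, H1, H2, H4, H8 and H12 and absolute change from V1-H0 at each post-dose hour. Use one column, because all subjects take 100 mg; Tables 25 and 28 already do this for concentration and the pharmacokinetic parameters.
2. State its population. The SAP Safety Set contains only randomised subjects, and randomisation is at V2, so anyone dosed on Day -7 who leaves before V2 is outside it. Either use the Safety Set and say so, or use all subjects dosed on Day -7 and declare this as an addition in SAP 6.
3. In Table 24, label the Visit 1 row as V1-H0.
4. Use the SAP 4.3 hour labels in Listing 23.
5. Reconcile the promised line graphs with the figures entry in SAP 5.2.2.2 and with the figure list in SAP 8.1.3.

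The cost is one extra table shell and a few label edits. The data are already scheduled, and the three multidose change time points are unaffected.

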5.2.3 Analysis of Other Variables

An analysis of the bioavailability evaluated in the first single dose phase of the study will be performed.

The following pharmacokinetic properties will be evaluated:

- Area under the curve (microg/ml x h) ≥ 5
- C_{max} (microg/ml x h) $\geq 0,8$
- T_{max} (hours) ≥ 3
- Elimination half-life ($t_{\frac{1}{2}}$)

The plasma concentration is recorded at Visit 1 at moment 0 (before COQUN intake), hour 1, hour 2, hour 4, hour 8 and hour 12.

Collected Variables

- Plasma concentration of coenzyme Q10 [CRF – Visit 1]

Derived Variables

The parameters AUC_t , AUC_{∞} , C_{max} , T_{max} , $t_{\frac{1}{2}}$ and their computation have been described in section 5.2.1 Primary Efficacy Analysis. Please refers to the mentioned section for details.

Analysis of Primary Efficacy variable:

Descriptive statistics such as mean \pm standard deviation, median with interquartile range, minimum, maximum and coefficient of variation will be presented for the plasma concentration of coenzyme Q10 at each time point in the entire sample of subjects. 95% confidence interval will be provided as well.

An explorative analysis on gender will be performed showing descriptive statistics for plasma concentration of coenzyme Q10 divided by gender. The effect of gender will be explored by means of a mixed model for repeated measures with covariates *gender*, time and the interaction term *gender*time*.

	Form	Form No.	1M-DMST-011-01-A1
	Statistical Analysis Plan	Page	Page 28 of 69
		Effective Date	07/05/2018

Change of plasma concentration versus baseline (i.e. change versus hour 0 values) will be computed for each study visit both for the whole sample and by gender. Change will be computed in the following way:

$$\text{Change (\%)} = \frac{\text{Value at Visit X} - \text{Baseline Value}}{\text{Baseline Value}} \times 100$$

Area under the curve, maximum concentration in the plasma, time of maximum concentration and terminal half-life and half-life will be presented descriptively on the original scale.

95% confidence interval will be provided for the means of the parameters AUC_t , C_{max} and T_{max} and terminal half life in the single dose phase i.e. following a single intake of COQUN oral formulation.

A concentration by time graph will be presented for the single dose phase in order to have a graphical visualization of the pharmacokinetics properties over time.

Line graphs will be provided for the concentration of coenzyme Q10 in the whole sample and by gender.

In performing statistical analysis, it is important to assess the statistical outliers. In fact, inclusion or exclusion of outlying subjects may lead to a different conclusion in assessment of differences in bioavailability between two formulations. It is therefore important to identify these outliers and study their effects.

Analysis will be evaluated on the ITT population and analysis will be replied on the PP population. Results obtained on the PP population will be considered as supportive of those obtained on the ITT set.

Imputations for missing values: No imputation of missing data will be performed

Analysis Sets to be used for:	Tables	ITT and PP analysis set
	Listings	ITT analysis set
	Figures	ITT and PP analysis set

Plasma concentration of coenzyme Q10 in the single dose phase will be summarized as follows:

Table 25. Plasma Concentration of Q10 in the Single Dose Phase (ITT Analysis Set)

Default summary statistics for plasma concentration of Coenzyme Q10 at each time point will be presented for the ITT analysis set.
This table will be replied on the PP analysis set.

Table 26. Plasma Concentration of Q10 in the Single Dose Phase by gender (ITT Analysis Set)

Default summary statistics per gender for the Plasma concentration of Coenzyme Q10 at each time point will be presented for the ITT analysis set.
This table will be replied on the PP analysis set.

Table 27. Change versus baseline by gender (ITT Analysis Set)

Default summary statistics by gender for the change versus baseline at each time point will be presented for the ITT analysis set.
This table will be replied on the PP analysis set.

	Form	Form No.	1M-DMST-011-01-A1
	Statistical Analysis Plan	Page	Page 29 of 69
		Effective Date	07/05/2018

Table 28.
Pharmacokinetic Parameters in the Single Dose Phase (ITT Analysis Set)

Default summary statistics for each pharmacokinetic parameter will be presented for the ITT analysis set together with confidence intervals at 95% for the means of the pharmacokinetics parameters.
 This table will be replied on the PP analysis set.

Plasma concentration of Q10 will be presented in subject data listings as follows:

Listing 24. Listing of Plasma Concentration of Q10 in the Single Dose Phase

A listing of the values for plasma concentration of Coenzyme Q10 in the single dose phase, sorted by screening number and within subjects by time point will be presented.

Listing 25. Listing of Pharmacokinetic parameters in the Single Dose Phase

A listing of the values for the pharmacokinetic parameters in the single dose phase, sorted by screening number will be presented.

Plasma concentration of Q10 will be presented in a graph as follows:

Figure 6. Concentration by time plot for the single dose phase (ITT Analysis Set)

A concentration by time graph will be presented for the single dose phase in the ITT analysis set. This plot will be replied in the PP analysis set.

Figure 7. Concentration by time plot by gender for the single dose phase (ITT Analysis Set)

A concentration by time graph will be presented for the single dose phase by gender in the ITT analysis set. This plot will be replied in the PP analysis set.

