Other reported side effects include rashes, nausea, upper abdominal pain, dizziness, sensitivity to light, irritability, headache, heartburn, and fatigue.

Medicines for high cholesterol (statins) and medicines that lower blood sugar cause a decrease of CoQ10 levels and reduce the effects of CoQ10 supplements. CoQ10 can reduce

	Study Title	Bioavailability Study of COQUN ORAL FORMULATION (CoQ10) administered in Healthy Adults (CoQ10-01)		
	Study ID	VF-BAQ10/2018	Sponsor:	VISUFARMA SpA
	Date	March 03, 2018	Vers.	Final

the body's response to the blood thinner (anticoagulant) medicine warfarin (Coumadin) and can decrease insulin requirements in people with diabetes.

Many factors can affect the Q10 blood level of people who are not taking a Q10 supplement: age, diet, disease, medications (for example, statin medications).

Q10 levels in the blood from the body's own synthesis of the substance increase after (0.20 ug/ml) birth until about the age of 21. Thereafter, the body's synthesis of Q10 gradually decreases.

It is expected that supplementing regularly with Q10 to raise the Q10 blood level, but much depends on the way in which the Q10 product has been prepared and much depends on the dosage. It was demonstrated that taking 30 milligrams or 50 milligrams of Q10 daily will not raise the Q10 level as much as taking 100 mg of Q10 daily will do, while taking 100 milligrams of Q10 twice daily will yield even greater gains in Q10 blood levels.

From the literature it is known that a well-absorbed Q10 supplement should over time raise the blood level to about 2.5 micrograms per milliliter if the individual is taking a 100-milligram dosage once a day, while if taken the same Q10 supplement in a dosage of 100 milligrams twice a day, its blood level should, over time, raise the steady-state Q10 blood level to somewhere in the area of 3.5 micrograms per milliliter. But, the attainable levels will vary from individual to individual, beside depending on the product itself as formulation.

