5.2 Efficacy Analysis

5.2.1 Primary Efficacy Analysis

The primary objective of this study is to evaluate the best dosage between 100mg once daily or 100mg twice daily for COQUN ORAL FORMULATION in order to reach a level of plasma concentration which might assure its antioxidant effect if taken on a regular basis.

The following pharmacokinetic properties will be evaluated:

- Area under the curve (microg/ml x h)
- C_{max}
- T_{max}
- Elimination half-life (t_{1/2})

Collected Variables

- Plasma concentration of coenzyme Q10 [CRF – Visit 2, 3, 4, 5]

	Form	Form No.	1M-DMST-011-01-A1
	Statistical Analysis Plan	Page	Page 21 of 69
		Effective Date	07/05/2018

Derived Variables

Derived variables are shown in Image 1 and are the following^[2,3]:

- AUC_t
The area under the plasma concentration curve to the last quantifiable concentration (C_t) at time t (AUC_t) will be determined by linear trapezoidal rule. The trapezoidal rule is a method used to numerically approximate the area under the concentration by time curve obtained by summing the area of all trapezoids constructed under the curve. Each trapezoid's area is obtained as:

$$\frac{(C_i + C_{i+1}) * (T_{i+1} - T_i)}{2}$$

where C_i is the concentration at time i (where i is any timepoint before the last observed timepoint T_t), C_{i+1} is the concentration at the following timepoint, T_i is the timepoint i and T_{i+1} is the following timepoint.

- C_{max}
Maximum concentration in the plasma (C_{max}) is obtained directly from the data being the highest plasma concentration value.
- T_{max}
 T_{max} is the collection time in which the maximum concentration is observed and is related to the drug absorption speed.
- $t_{\frac{1}{2}}$
The terminal half-life is defined as the time required for the plasma concentration of a drug to decrease 50% in the final stage of its elimination; this parameter is computed with the formula^[2]:

$$t_{\frac{1}{2}} = \frac{\ln 2}{\lambda_z}$$

where λ_z is the smallest elimination rate constant observed which is obtained as the ratio of clearance and volume of distribution. Clearance is calculated as the ratio of dose and AUC while volume of distribution is obtained as dose divided by concentration at time 0 that is the concentration registered after the first intake of coenzyme (in the single dose time 0 is hour 1, in the multidose phase time 0 is visit 2).

[figure not shown]

Image 1. Pharmacokinetic parameters

	Form	Form No.	1M-DMST-011-01-A1

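### Single-dose phase: the SAP prints the Cmax threshold in an area unit, and a confidence interval for mean Tmax is a poor guide to a 3 h criterion on a 0, 1, 2, 4, 8, 12 h sampling grid

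*SAP*

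**What the plan says.** Protocol 7.2 and 12.7 list the pharmacokinetic properties as the primary variables. Thresholds are attached to three of them: AUC at least 5 (microg/ml x h), Cmax at least 0.8 and Tmax at least 3. Neither the Cmax nor the Tmax threshold has a unit there.

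SAP 5.2.3, which covers the single-dose phase, repeats the thresholds and adds units. The first line reads "Area under the curve (microg/ml x h) ≥ 5". The next begins "C_{max} (microg/ml x h", the same unit, now set against 0.8. Tmax is given in hours.

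The definitions are in SAP 5.2.1. Cmax "is obtained directly from the data being the highest plasma concentration value". Tmax "is the collection time in which the maximum concentration is observed". In the single-dose phase, concentration is "recorded at Visit 1 at moment 0 (before COQUN intake), hour 1, hour 2, hour 4, hour 8 and hour 12".

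On inference, SAP 5.2.3 says that a "95% confidence interval will be provided for the means of the parameters" AUC, Cmax, Tmax and half-life. No method for the interval is named. The Table 28 shell prints n, mean, SD, 95% CI, CV, median, interquartile range, minimum and maximum for each parameter. It has no row for meeting a threshold, and neither document says whether a threshold applies to each subject, to the mean or to the median.

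**The concern.** Three things do not fit together.

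- **Cmax.** A concentration cannot be compared with a limit expressed as concentration multiplied by time. The SAP is the only place where a unit for this limit appears, and that unit conflicts with the SAP's own definition.
- **Tmax limit.** The limit of 3 h is not a sampling time, so a report that the criterion is met could be read as evidence about 3 h that the design does not collect.
- **Tmax interval.** The only measure of uncertainty planned for Tmax is an interval for the mean. The grid steps widen from 1 h to 4 h, so a minority of late peaks can move the mean well past 3 h.

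At stake is how one listed primary-variable threshold is read, and whether the reported interval describes what most subjects did. Protocol 10.8 makes further studies depend on positive results from this one.

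**Working it through.** **1. Cmax unit.** The SAP 5.2.1 definition makes Cmax one of the measured concentrations. Protocol 6.1 expresses blood levels in micrograms per millilitre (a well-absorbed supplement taken once daily should "raise the blood level to about 2.5 micrograms per milliliter"), and both abbreviation lists include ug/ml. AUC is concentration multiplied by hours, so microg/ml x h is right for the threshold of 5 and wrong for the 0.8. Read with the definition, the limit is 0.8 microg/ml. The number does not change.

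**2. Tmax criterion on the grid.** The possible observed values are 0, 1, 2, 4, 8 and 12 h. Those satisfying Tmax >= 3 are 4, 8 and 12. Those satisfying Tmax >= 4 are the same three, as they are for any cut-off above 2 h and up to 4 h. The rule is decidable for every subject but has no resolution at 3 h.

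**3. Mean against the majority.** The documents give no expected Tmax distribution and no result to reproduce, so what follows is illustration with n = 24 (protocol 12.3).

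Suppose 14 subjects peak at 2 h and 10 at 8 h.

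- Mean = (14 x 2 + 10 x 8)/24 = 108/24 = 4.5 h.
- Sum of squares = 14 x 2.5² + 10 x 3.5² = 87.5 + 122.5 = 210.
- SD = √(210/23) = 3.02; SE = 3.02/√24 = 0.617.
- 95% CI, assuming the t form with 23 df (2.069): 4.5 ± 1.28, or 3.2 to 5.8 h.
- Median = 2 h.
- Proportion meeting the criterion = 10/24 = 42%. Exact (Clopper-Pearson) 95% CI 22% to 63%.

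The interval for the mean excludes 3 h from above, yet 58% of subjects fail the criterion. Protocol 12.1 specifies 90% intervals where the SAP uses 95%. At 90% (t = 1.714) the interval is 4.5 ± 1.06, or 3.4 to 5.6 h, and the conclusion is the same.

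**4. How far this extends.** Put the remaining subjects at 2 h and vary the number and time of the late peaks.

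| Late peaks at | Smallest number of 24 giving mean >= 3 h | Smallest number giving a 95% t interval wholly above 3 h |
|---|---|---|
| 4 h | 12 (mean 3.00) | not reached with a minority |
| 8 h | 4 (mean 3.00) | 10 (lower limit 3.22; with 9 it is 2.997) |
| 12 h | 3 (mean 3.25) | 8 (lower limit 3.30; with 7 it is 2.96) |

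The disagreement needs a sizeable minority peaking at 8 h or later. If late peaks are at 4 h, the mean reaches 3 h only when half the subjects do.

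**The case against.** The strongest reply is that little goes wrong in practice.

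- The Cmax unit is a slip with one sensible reading. No computation uses it, and Table 28 prints neither unit nor threshold. This stands: it is a labelling correction, still needed because no other unit is stated.
- A cut-off between two sampling times is not an error. This also stands.
- Table 28 already shows median, interquartile range and range, and Listing 25 gives every subject's Tmax, so in the illustration a reader would see a median of 2 h beside the mean of 4.5 h. This largely stands. What is missing is the count at each sampling time and any interval for the quantity that the criterion concerns.
- Protocol 12.6 pre-specifies no hypotheses, the SAP presents these parameters descriptively, and it files the single-dose analysis under other variables. This stands and limits the consequence. The OD versus BID comparison is not affected.

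Two stronger readings are tempting, and the documents support neither. A reader might infer that two of the three thresholds cannot be applied at all. They can: Tmax >= 3 h picks out 4, 8 and 12 h without ambiguity, and the definition of Cmax settles its unit. A reader might also infer that peaks near 3 h will be misclassified at some material rate. The documents give no assay precision, adult baseline level or half-life from which to size that, and restating the criterion as 4 h or later selects the same subjects, so it would not change the rate.

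**Conclusion.** The point holds as a modest correction. The unit printed for the single-dose Cmax threshold contradicts the SAP's own definition; 0.8 microg/ml is the reading that fits, for the sponsor to confirm. The Tmax criterion is usable per subject but amounts to an observed peak at the 4 h sample or later. The only planned interval for Tmax addresses the mean, and it can lie above 3 h when as few as 10 of 24 subjects (late peaks at 8 h) or 8 of 24 (late peaks at 12 h) meet the criterion.

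Those counts assume a t-based interval, which the SAP does not name, and two-point Tmax distributions chosen for illustration. They show what can happen, not what is likely for this product. With no formal decision rule in the plan, the effect is on how the result is read and reported.

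**What to change.** 1. In SAP 5.2.3, change the Cmax unit to microg/ml once the sponsor has confirmed it, and state the same unit beside the 0.8 in protocol 7.2 and 12.7.
2. State the Tmax criterion on the sampling grid, as largest concentration observed at the 4 h sample or later, and say that it applies to each subject.
3. In Table 28, keep the median and range for Tmax. Add the number of subjects peaking at each sampling time, and the proportion at 4 h or later with its CI and the method named. Do not base the reading of Tmax on the mean and its CI.

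The cost is a few words in each document and one revised table shell. No new samples or data are needed.
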